2.6 Potential Risks

Human CC10 is a natural product of respiratory epithelia and is normally present in the extracellular fluid of the lung, as well as amniotic fluid. The clinical protocol proposes to supplement low endogenous CC10 levels in the lungs of premature neonates with a recombinant human protein. Thus, we do not expect immunogenicity to be a problem. Peak concentrations of rhCC10 in lung fluid and blood of infants to be treated may exceed normal adult levels, but should be well within the ranges explored in non-clinical pharmacology and toxicology studies. rhCC10 has been tested in non-clinical toxicology studies at doses up to 25 mg/kg (IT) and 2 mg/kg (IV).

CC10 is transcriptionally upregulated in the lungs by corticosteroids. Therefore, patterns of toxicity secondary to excessive CC10 that could occur secondary to treatment with corticosteroids were specifically examined in the first study in preterm infants and in all animal pharm/tox studies. Although no such toxicities have been detected, these effects will continue to be monitored closely in the present studies.

The pharmacokinetic analysis of CC10 in TAF fluids in the first trial demonstrated a trend that native CC10 expression was higher in day 3 TAF of placebo infants than in CC10-treated infants. Although the number of day 3 TAF samples was extremely limited (n=2-3/group due to many infants

being extubated), there is a possibility that administration of exogenous rhCC10 may transiently suppress expression of the native protein in the lungs. This will be closely monitored during the present trial.

There was a higher incidence of confirmed (n=3) and suspected (e.g. radiologic; n=5) NEC in rhCC10-treated infants compared to the placebo group (P=NS). This was not thought to be due to administration of study drug, since the NEC occurred 3-6 weeks after rhCC10 administration and because other infants in the NICU who were not enrolled in the study also developed NEC at the same time. (NEC is known to occur in clusters). However, the incidence and severity of NEC, as well as other infectious related AEs (e.g. sepsis, pneumonia, etc.) will be closely monitored during this study.

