7.2 Reporting of Serious, Life-Threatening or Unexpected Adverse Events

Serious and Unexpected Adverse Events. Adverse Events that are either serious and/or unexpected must be reported to the Sponsor and CRO as soon as possible after the occurrence. Such events must be reported by the Sponsor to the FDA in writing as soon as possible after the occurrence but in no case more than 7 days (expedited) or 15 days (non-expedited) after the Sponsor's initial receipt of the information.

Unexpected and Fatal or Life-Threatening Adverse Events. Adverse Events that are unexpected and are life-threatening or result in death must be reported to the Sponsor as soon as possible after occurrence. Such events must be reported by the Sponsor to the FDA by facsimile, mail, email, and/or by courier as soon as possible after the occurrence, but in no case more than 7 days after the Sponsor's initial receipt of the information.

All serious, life-threatening, or unexpected adverse events will be reported to the Medical Monitor and to the CRO within 24 hours of the site becoming aware of the event using the CRO's secured e-mail portal.

7.3 Serious Adverse Event Reporting.

Some Adverse Events are of particular importance or concern in the patient population being treated. The purpose of monitoring Serious Adverse Events is to allow the independent DSMB to suspend enrollment in the study if there appears to be a higher incidence of such events among the treated patients than would be expected in a comparable group of premature infants (a difference may be considered clinically significant even though it is not statistically significant due to small patient numbers).

For the purposes of this study, the following will be considered Serious Adverse Events:

- Air leak, including pneumothorax, pulmonary interstitial emphysema (PIE) and, pneumomediastinum significantly impairing gas exchange;
- Pulmonary hemorrhage (requiring blood products and escalating ventilator support);
- Grades III/IV IVH, PVL, seizures;
- Confirmed NEC (\geq Bells stage II, based on attending Neonatologist diagnosis);
- ROP Stage 3 or 4;
- Overwhelming sepsis (early and late – associated with shock);
- Pneumonia
- Death

7.4 Additional Adverse Event Reporting.

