The population to be studied in this protocol is at high risk for morbidities associated with prematurity. Events listed below will, for the purposes of this clinical trial, be considered events commonly associated with prematurity. The following morbidities associated with prematurity will be entered on the CRF.

- Air leak syndrome (e.g. pulmonary interstitial emphysema, pneumothorax, pneumomediastinum)
- Anemia of prematurity
- Apnea of prematurity
- Bradycardia
- Periventricular leukomalacia (confirmed by cranial ultrasound)
- Gastrointestinal perforation (confirmed by radiology and surgical pathology to not be associated with necrotizing enterocolitis)
- Hyperbilirubinemia
- Necrotizing enterocolitis (confirmed by radiology; < Bells Stage II)
- Patent ductus arteriosus (confirmed by echocardiography)
- Periventricular or intraventricular hemorrhage (confirmed by cranial ultrasound – grades I, II)
- Sepsis (culture-confirmed from sterile site e.g., blood, CSF, urine)
- Retinopathy of prematurity (Stage II only)

Adverse Events of Nosocomial Infection (specific definitions)

Since rhCC10 is an immunomodulatory protein, special attention will be paid to the AEs associated with nosocomial infection, with a particular emphasis on sepsis, pneumonia, NEC, UTI, and meningitis. A diagnosis of nosocomial infection may be difficult in an intubated neonate and definitions vary. It is recognized that an inflammatory process can arise in the absence of infection. Since uniform reporting is required, the terms sepsis and pneumonia should be reserved for those AEs meeting the criteria defined in Appendix A. In the absence of documented infection, manifestations of a systemic inflammatory response should be listed by underlying etiology or by symptom. Separate summaries of adverse events associated with nosocomial infection will be evaluated on an ongoing basis by the site investigators and the Sponsor and reported to the DSMB, the site IRBs, and FDA as soon as possible after recognition of their importance.

7.5 Criteria for Suspension of the Trial (Stopping Rules).

The DSMB will receive information on the occurrence of Serious Adverse Events on an ongoing basis as patients are enrolled and treated in the study. They will receive the reports and the assignment of infants to groups A, B, or C. If serious adverse events are increased in one group

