8.4 Secondary Endpoints: Safety and Efficacy - Adverse Events

The safety of the study drug will continue to be assessed by comparing the incidence of adverse events and serious adverse events in the treatment and placebo groups to each other and to the historical incidence of the adverse events at each institution. Safety evaluations will include all serious adverse events up to at least 12 months CGA, and routine laboratory monitoring prior to NICU discharge (CBC, electrolytes, liver function studies, urinalysis, head ultrasound). In addition to evaluating the safety of rhCC10, preliminary efficacy of rhCC10 in this patient population may also be indicated by decreases in the numbers of all SAEs and/or specific types of SAEs (ie. IVH, PVL, ROP, sepsis, infection, etc.).

8.5 Statistical Considerations.

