Power Analysis: A total of 88 preterm infants will be randomized to placebo, lower dose, or higher dose rhCC10 with an allocation ratio of 2:1:1. The primary analysis will be the comparison of placebo versus both rhCC10 dose groups combined. The prior trial demonstrated that the two doses are likely to yield similar results. Two doses will be used for the purpose of extending the safety profile for each individual dose, as that safety data may facilitate the choice of dose for a future Phase III confirmatory study. For SAEs or AEs with background rates of 5%, 10%, or 15%, the sample size of 22 in either dosing group will provide a probability of observing it of 68%, 90%, and 97%, respectively. The proposed trial is powered for the comparison of the two doses combined versus placebo for the composite endpoint of death or development of CRM. Secondarily, the study will yield effect size estimates for each individual dose versus placebo. Our assumptions regarding the comparison of placebo versus rhCC10 are based on the previous study with 7 placebo, 8 lower dose, and 7 higher dose infants (one infant in each of the rhCC10 treatment groups died). It is important to address the combined endpoint of death or re-admission to the hospital for respiratory problems. In the previous study, one loss-to-follow-up occurred in each of the three experimental groups and one death occurred in each of the rhCC10 groups. At 6 months, 3 of the 6 infants on placebo with follow-up were re-admitted to the hospital for respiratory problems and none of the 11 subjects treated with either rhCC10 dose with follow-up data were re-hospitalized. A realistic and conservative assumption for the 3 lost-to-follow-up babies is that they all either died or had respiratory disease. Then the proportions with disease or death on placebo and rhCC10 are assumed to have been 0.57 and 0.27. If the proportions in the proposed study are similar, with 44 subjects on placebo and 44 subjects in the two dose groups combined, power will be 82% with $\alpha=0.05$. nQuery Advisor version 6 was used.

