APPENDIX A: DEFINITIONS OF SPECIFIC ADVERSE EVENTS
CRITERIA FOR ADVERSE EVENTS ASSOCIATED WITH NOSOCOMIAL INFECTION,
AIR LEAKS AND PULMONARY HEMORRHAGE

1. Sepsis

A number of terms confuse the definition of sepsis, including infection, bacteremia, sepsis syndrome, and septic shock. For the purpose of this study, only the term sepsis should be used for AE reporting. Sepsis occurring in the first 3 days after birth (early onset) is considered congenital and should be recorded under past medical history, not as an AE. Sepsis will be defined as the systemic inflammatory response to infection, with criteria adapted from the Centers for Disease Control (CDC) Surveillance of Nosocomial Infection Control Program. All infants with suspected sepsis should have at least 2 sets of blood cultures from 2 separate sites, a urine culture and a cerebral spinal fluid (CSF) culture, with other cultures as determined by the investigator. If a central line is in place, one blood culture should be drawn from the central line (if possible) and one peripherally. A diagnosis of sepsis will require meeting at least one clinical sign or symptom, one invention survey, and one therapy condition.

Definition of nosocomial sepsis

Clinical signs/symptoms Criteria- must meet at least one

Lethargy

Fever ($>38^{\circ}\text{C}$), hypothermia ($<37^{\circ}\text{C}$) or temperature instability

Apnea (increase in frequency and severity from baseline)

Bradycardia (<100 beats/min) or tachycardia (>170 beats/min) (increase frequency and severity from baseline)

Hypotension (mean bp > 10 mm hg below the gestational age with capillary refill time > 5 secs and/or metabolic acidosis on a blood gas)

Oliguria (<1 ml/kg/hour over a 12 hour period)

Infection survey Criterion – must meet

No apparent infection or alternative cause at another site

Therapy Criterion – must meet

Anti-infective drugs given for ≥ 4 days

While all cases meeting the definition of nosocomial sepsis must be recorded as AEs, additional information will be collected on each episode to permit classification of the diagnosis into definite, probable, and no agent identified. Criteria for confirmation of a case of definite sepsis require microbiologic confirmation of an infecting organism. All cases of definite sepsis must meet one of the

criteria defined above. In addition to meeting the definition of nosocomial sepsis, cases of probable sepsis will have one positive blood culture for coagulase negative staphylococcus.

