Criteria for the confirmation of a diagnosis of definite sepsis

One blood culture positive for all bacterial, viral, and fungal pathogens other than coagulase negative staphylococcus.

Two positive blood cultures coagulase negative staphylococcus

One positive blood culture and one culture from an otherwise sterile site (CSF, joint, pleural, or peritoneal fluid, bone or deep tissue abscess material) Coagulase negative staphylococcus; urine is excluded as a sterile site unless from a suprapubic tap

Nucleic acid testing, Latex fixation, or PCR assay

Diagnostic single-antibody titer (IgM) or 4-fold increase in paired sera (IgG) for pathogen

2. Pneumonia

Although pneumonia is an important nosocomial infection in the NICU, the diagnosis is often difficult to make due to the inadequacies of current diagnostic methods. For the current trial, pneumonia will be more rigorously defined according to the Centers for Disease Control prevention algorithm. Pneumonia occurring in the first 3 days after birth (early onset) is considered congenital and should be recoded under past medical history, not as an AE. All AEs of pneumonia must meet at least one radiographic, one gas exchange, and 3 clinical or vital signs criteria listed below. **Respiratory manifestations not meeting these criteria should be listed by an alternative etiology (i.e. pneumothorax, aspiration, sepsis, etc.) or by symptom (i.e. apnea, bradycardia).**

Definition of nosocomial pneumonia

Radiographic Criteria – must meet at least one

Persistent new or progressive infiltrate consistent with infection (interstitial, bronchial, or alveolar)

Consolidation

Cavitation

Abscess

Pneumatocele

Gas exchange Criteria – must meet at least one

Oxygen desaturation episodes (increased in frequency and severity from baseline)

Increased oxygen requirement of at least 10 percentage points

Increased ventilation requirement

Clinical/vital signs Criteria – must meet at least 3

Cough

Wheezing, rales or rhonchi

Apnea, tachypnea, nasal flaring with retraction of chest wall, or grunting

New onset of lower respiratory tract secretions, change in character of secretions, or increase in the quantity of secretions or suctioning requirements

Temperature instability

Bradycardia (<100 beats/min) or tachycardia (>170 beats/min)

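### Appendix A files all sepsis and pneumonia of the first 3 days as past medical history, even with onset after dosing, and contradicts the SAE list in Section 7.3

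*Combined protocol and SAP*

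**What the plan says.** Appendix A, item 1: "Sepsis occurring in the first 3 days after birth (early onset) is considered congenital and should be recorded under past medical history". Item 2 repeats the rule: "Pneumonia occurring in the first 3 days after birth (early onset) is considered congenital and should be recoded under past medical history". Both sentences go on to say that the event is not to be entered as an AE. The clock runs from birth, and neither sentence mentions dosing or shock.

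Section 7.3 lists among the SAEs "Overwhelming sepsis (early and late – associated with shock") and also pneumonia, the latter with no limit on onset. Section 7.4 lists as a CRF entry "Sepsis (culture-confirmed from sterile site e.g., blood, CSF, urine"), again with no onset limit, but then reserves the words sepsis and pneumonia for AEs that meet Appendix A.

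The stated intentions are these:
- Section 7.4: "Since rhCC10 is an immunomodulatory protein, special attention will be paid to the AEs associated with nosocomial infection".
- Section 2.6, after discussing NEC: "as well as other infectious related AEs (e.g. sepsis, pneumonia, etc.) will be closely monitored during this study".
- Section 8.4: safety is "assessed by comparing the incidence of adverse events and serious adverse events in the treatment and placebo groups".
- Section 8.5, taking three background event rates (5%, 10% and 15%) in turn, states: "the sample size of 22 in either dosing group will provide a probability of observing it of 68%, 90%, and 97%, respectively".

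On timing, infants are enrolled at 24 hours of age or less (5.1). They receive one dose on the day of birth (Table 1), between 30 minutes and 4 hours after surfactant (6.3). Table 2 collects AEs from day 1, which it defines as the day of birth.

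**The concern.** A 3-day cutoff is a reasonable way to label an infection as congenital or nosocomial. Here it does a second job: it decides whether an infection that begins after an experimental intratracheal dose counts as an AE at all. For a drug that the protocol itself calls immunomodulatory, the days just after instillation should not be left out of the AE record.

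Two consequences follow. First, if Appendix A is applied, early post-dose sepsis and pneumonia leave the between-arm comparison in 8.4, and those that would be SAEs leave the group comparison the DSMB makes under 7.5. Section 8.4 also allows a fall in SAEs, with sepsis and infection named, to be read as preliminary efficacy, so the omission affects the benefit reading as well as the harm reading. Second, since 7.3 points the other way for early septic shock, two sites can classify the same event differently.

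**Working it through.** **1. The texts side by side**

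| Event in the first 3 days, onset after dosing | Appendix A | Sections 7.3 and 7.4 |
|---|---|---|
| Sepsis with shock | Medical history, not an AE | SAE, early or late (7.3) |
| Culture-confirmed sepsis without shock | Medical history, not an AE | CRF entry with no onset limit (7.4), but the term is reserved for AEs meeting Appendix A |
| Pneumonia | Medical history, not an AE | SAE with no onset limit (7.3), but the term is reserved for AEs meeting Appendix A |

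Section 7.1 defines an SAE as an AE with certain outcomes, so the first row is a direct contradiction. The other two rows are less direct: a short list and a governing definition can be read together, but sites could apply either rule.

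**2. Does the 3-day period extend past dosing?**

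If 3 days means 72 hours of age (assumption), the post-dose time covered by the rule is 72 minus age at dosing:
- dose at 0.5 h (surfactant at birth plus the 30-minute minimum): 71.5 h
- dose at 24 h: 48 h
- dose at 28 h (surfactant at 24 h plus 4 h, an extreme that sits poorly with the rule of no study medication after the first day of life): 44 h

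If calendar days are meant and birth is late on day 1, the period could end near 48 h of age. That leaves 47.5, 24 and 20 h. The window is positive in every case.

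**3. The plan's own detection figure**

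The probability of at least one event in n infants is 1 − (1 − p)^n. With n = 22:
- p = 0.05: 1 − 0.95^22 = 67.6%
- p = 0.10: 1 − 0.90^22 = 90.2%
- p = 0.15: 1 − 0.85^22 = 97.2%

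These reproduce the stated 68%, 90% and 97%.

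**4. The same figure with early events filed as history**

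If a share e of the events is early and not recorded as AEs, the probability becomes 1 − (1 − p(1 − e))^n. The documents give no value for e, so the shares below are assumptions. With p = 0.10:

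| e | n = 22 | n = 44 (both doses combined) |
|---|---|---|
| 0 | 90.2% | 99.0% |
| 0.10 | 87.4% | 98.4% |
| 0.25 | 82.0% | 96.8% |
| 0.50 | 67.6% | 89.5% |
| 0.75 | 42.7% | 67.2% |
| 1 | 0% | 0% |

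The last row applies to early-onset sepsis or pneumonia taken as an event in its own right: under Appendix A it cannot appear in the AE tables.

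**5. How much drug exposure falls in the window**

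Section 2.4 gives a half-life of 9–11 h after mucosal dosing and 2–2.5 h in the circulation. I assume these apply to the infants. The exposure share by t hours after dosing is then 1 − 0.5^(t/h) with h = 9–11 h. With both phases, at rates ks (slow) and kf (fast), it is 1 − (kf·exp(−ks·t) − ks·exp(−kf·t))/(kf − ks). The ranges over both models are:
- cutoff at 72 h of age: 91.9–96.6% (t = 44 h), 93.7–97.5% (t = 48 h), 98.6–99.6% (t = 71.5 h)
- cutoff at 48 h of age: 63.4–84.3% (t = 20–24 h), 93.5–97.4% (t = 47.5 h)

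This is a share of exposure, not of infection risk. It shows only that the window coincides with most of the systemic exposure, and the contradiction does not depend on it.

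**The case against.** The best defence is that the rule is deliberate. Infection in the first days is often acquired before or during birth, Appendix A is headed as covering nosocomial infection, and the special attention promised in 7.4 is to nosocomial infection. The rule applies equally to every arm, so it does not by itself bias the comparison. The events stay on record as medical history. Deaths remain SAEs, life-threatening events are SAEs under 7.1 whatever their relation to the drug, and NEC, UTI and meningitis have no 3-day rule. Appendix A also says that all cases meeting its nosocomial definitions must be recorded as AEs, and the listed criteria carry no onset limit. Finally, the early shares have no source, and at a 10% share detection falls only from 90.2% to 87.4%.

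Much of this limits the size of the problem, and the early shares are indeed only illustrative. None of it removes the problem. The sentence on all nosocomial cases and the life-threatening rule in 7.1 are further texts that pull against the 3-day rule; they do not reconcile it with 7.3. The congenital label is a judgement about cause, and 7.1 says relatedness does not decide SAE status. Infants with evidence of congenital infection are excluded at entry (5.2), so an infection first evident after dosing was not evident at enrolment. Equal application across arms prevents a differential recording rule, but it does not recover a drug effect that appears in the unrecorded window. Section 2.6 promises monitoring of sepsis and pneumonia without restricting it to nosocomial cases.

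**Conclusion.** The concern holds. Early overwhelming sepsis is an SAE in Section 7.3 and not an AE in Appendix A, and nothing in the documents reconciles the two. The pneumonia entry in 7.3 and the sepsis entry in 7.4 conflict with Appendix A less directly. The post-dose gap follows from the wording and the dosing schedule alone.

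The loss of safety information cannot be sized from the documents. It is complete for early-onset sepsis and pneumonia in the AE tables if Appendix A is followed. For sepsis or pneumonia overall it depends on the unknown early share: from slight at 10% to about half the detection probability in a single dose group at 75%, for an event with a 10% rate. The primary efficacy analysis and the sample size are untouched. This should be fixed, because a stated rule takes post-dose events out of the safety comparison of an immunomodulatory drug.

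**What to change.** Reconcile Sections 7.3 and 7.4 with Appendix A, items 1 and 2:
- Keep as medical history only sepsis or pneumonia with onset before instillation.
- Record onset after instillation as an AE, and as an SAE where 7.1 or 7.3 applies.
- Keep the congenital/nosocomial distinction as a CRF flag for early onset (up to 72 h of age), and state the 3-day limit in hours of age.
- Tabulate early and late events separately by arm.

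The cost is amendment wording, one onset-time field on the CRF and one additional AE table. Onset has to be timed within hours in infants already ventilated for RDS, so the CRF instructions need a convention for onset that cannot be placed relative to instillation. Because evidence of congenital infection is an exclusion, the medical-history category will probably be small. More background early-onset infections will be reported in all arms, some probably acquired before dosing; the 44 placebo infants supply the reference rate.

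### Appendix A's sepsis definition requires 4 days of anti-infective treatment with no exception for death, and it conflicts with the sepsis entries in sections 7.3 and 7.4

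*Combined protocol and SAP*

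**What the plan says.** Appendix A, item 1, builds nosocomial sepsis from three parts, all required: "A diagnosis of sepsis will require meeting at least one clinical sign or symptom, one invention survey, and one therapy condition" (the second part is evidently the infection survey). The therapy part is marked as compulsory and reads "Anti-infective drugs given for ≥ 4 days". Nothing is said about an infant who dies or is transferred before the fourth day. Sepsis in the first 3 days after birth is sent to medical history and is not an AE.

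Section 7.4 ties AE coding to this definition: "the terms sepsis and pneumonia should be reserved for those AEs meeting the criteria defined in Appendix A". It calls for separate summaries of nosocomial-infection events, reported to the DSMB, the IRBs and FDA, because the study drug is immunomodulatory.

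Two other entries name sepsis without a treatment duration. Section 7.3 lists as an SAE "Overwhelming sepsis (early and late – associated with shock". The list of prematurity morbidities in section 7.4 has a CRF entry for sepsis confirmed by culture from a sterile site. Section 8.4 then says that preliminary efficacy may be indicated by "decreases in the numbers of all SAEs and/or specific types of SAEs (ie. IVH, PVL, ROP, sepsis, infection, etc".

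**The concern.** A minimum course of treatment is a reasonable way to screen out short empirical courses that are stopped once infection is ruled out. It does not suit an infant whose treatment ended because the infant died. For that infant the 4-day rule makes survival on treatment part of the definition of the event.

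Survival to day 4 of treatment happens after randomization and could be affected by the study drug. If sepsis were more often rapidly fatal in one arm, that arm's count of Appendix A sepsis would fall for that reason alone. Infection is the safety topic singled out in section 7.4, and section 8.4 allows fewer sepsis events to be read as a favourable sign. A count that can fall because of early deaths is a poor basis for either use.

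**Working it through.** **Reading the rules together.** Take an infant in week 3 with shock and a positive blood culture who dies 36 hours after anti-infectives start.

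| Provision | Treatment duration required? | Does this infant count? |
|---|---|---|
| Appendix A, nosocomial sepsis | Yes, 4 days | No |
| Section 7.4, use of the term sepsis | Through Appendix A | No |
| Section 7.4, culture-confirmed sepsis on the CRF | None stated | Yes |
| Section 7.3, overwhelming sepsis SAE | None stated | Yes |
| Section 7.3, death SAE | None | Yes, as a death |

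No other infection label is clearly open. Appendix A rejects related terms such as bacteremia and septic shock for AE reporting in favour of sepsis alone. The fallback in section 7.4, "In the absence of documented infection, manifestations of a systemic inflammatory response should be listed by underlying etiology or by symptom", is for events without documented infection, and this infant has a positive culture.

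**Does a positive culture rescue the case?** For probable sepsis, no: "In addition to meeting the definition of nosocomial sepsis, cases of probable sepsis will have one positive blood culture for coagulase negative staphylococcus". For definite sepsis the text is unclear. The sentence beginning "All cases of definite sepsis must meet one of the" goes on to criteria defined above. That could mean any one part of the definition, which would let a culture-positive case in without 4 days of treatment. The matching pneumonia sentence points below, to its microbiological list, so the more natural reading adds a laboratory requirement to an episode that already qualifies. Two sites could code the same infant differently. Appendix A's pneumonia definition has no treatment-duration criterion, so the problem is specific to sepsis.

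**The plan's own detection figures.** Section 8.5 gives the chance of seeing at least one event among 22 infants as 68%, 90% and 97% at rates of 5%, 10% and 15%. The formula 1 − (1 − p)^22 gives 67.6%, 90.2% and 97.2%, so these reproduce.

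**Size, on assumed inputs.** The documents give neither a sepsis rate nor the share of septic infants who die before day 4. I use the plan's illustrative rates p and an assumed early-fatal share f of 10%, 20% or 30%. Expected cases lost among 88 infants are 88 × p × f. The chance of at least one counted case in a dose group of 22 is 1 − (1 − p(1 − f))^22.

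| Rate p | Cases lost of 88 (f = 10%, 20%, 30%) | Detection with no loss | Detection (f = 10%, 20%, 30%) |
|---|---|---|---|
| 5% | 0.4, 0.9, 1.3 | 67.6% | 63.7%, 59.3%, 54.3% |
| 10% | 0.9, 1.8, 2.6 | 90.2% | 87.4%, 84.0%, 79.7% |
| 15% | 1.3, 2.6, 4.0 | 97.2% | 95.9%, 94.0%, 91.3% |

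**Direction, on assumed inputs.** The counted rate is p(1 − f). Suppose true sepsis is 25% on placebo and 30% on rhCC10, with 10% early-fatal on placebo, so placebo is counted as 0.25 × 0.90 = 22.5%.
- 10% early-fatal on rhCC10: 0.30 × 0.90 = 27.0%. The excess keeps its ratio.
- 20%: 0.30 × 0.80 = 24.0%. The excess shrinks.
- 30%: 0.30 × 0.70 = 21.0%. The excess appears as a deficit.

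The sign changes only when the early-fatal share on rhCC10 exceeds 1 − 0.225/0.30 = 25%. With true sepsis of 35% on rhCC10 and 30% early-fatal, the counted rate is 24.5%, still above placebo. Reversal is therefore possible but needs a marked difference between arms in early fatality.

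**The case against.** A reader might infer that rapidly fatal sepsis cannot be recorded as sepsis anywhere, and that the worst cases drop out of a key infection endpoint. The documents do not support that. The infant in the example fits both the 7.3 SAE and the 7.4 CRF entry, and the definite-sepsis sentence can be read as a way in. The plan has no key infection endpoint: section 8 is headed as exploratory, and sepsis is one of several SAE types named in section 8.4. If the 7.3 entry governs that comparison, the 4-day rule does not touch it.

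Nor would the deaths be hidden from the DSMB. Death is an SAE, section 1.2 gives the DSMB all adverse experiences, and under section 7.5 it receives SAEs by group and may suspend enrollment on medical judgment without statistical significance.

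A reader might also build a striking figure: with 11 true cases per arm and 3 lost from one arm only, 8 against 11 looks like a 27% reduction (1 − 8/11). That rests on an assumed rate and on every loss falling on one side. If losses were unrelated to arm, three out of three falling in the same arm would have probability 2 × (1/2)³ = 0.25. Even then, 8/44 against 11/44 gives a Fisher p of 0.61. The figure does not measure the likely effect.

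What remains is that section 7.4 sends coders to Appendix A for the term sepsis, Appendix A has no exception for death, and no rule ranks it against the two entries without a duration.

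**Conclusion.** The point holds as a gap in event classification and an unresolved conflict among section 7.3, section 7.4 and Appendix A. Followed literally, the section 7.4 rule leaves a rapidly fatal late-onset sepsis out of the nosocomial-infection summaries. The death itself is reported; its attribution to infection can be lost, and possibly unequally between arms. Whether the section 8.4 comparison is affected depends on which definition governs, which the documents do not settle.

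The number affected is unknown and probably small: about 0.4 to 4 of 88 infants at rates of 5% to 15% and an assumed early-fatal share of 10% to 30%. With groups of 22 and 44, even a few misclassified deaths matter when an infection signal is being judged. The change is worth making because it costs little, not because a large bias has been shown.

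**What to change.** These are rules for classifying events; patient care does not change.

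1. In Appendix A, count the therapy criterion as met when anti-infective treatment for suspected sepsis had been started and was ongoing at death before day 4. Keep the clinical-sign and infection-survey criteria as requirements.
2. State that this also holds for culture-positive (definite) cases, which removes the ambiguity in that sentence.
3. In the nosocomial-infection summaries, report culture-positive and culture-negative early deaths separately, so that the effect of the new clause is visible.
4. Reconcile sections 7.3 and 7.4 with Appendix A and say which definition feeds each summary and the section 8.4 comparison. Cover early-onset sepsis, which 7.3 includes and Appendix A sends to medical history. Do not narrow the 7.3 SAE to the Appendix A definition, since that would remove early-onset events that 7.3 now captures.

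The cost is a clause in Appendix A, matching CRF guidance and a short cross-reference. The downside is that a few deaths from other causes in infants on empirical antibiotics may be counted as culture-negative sepsis. The class with no agent identified cannot tell these from true culture-negative sepsis, so the separate reporting in item 3 is needed.
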